7.5 Analysis Populations

7.5.1 Intention to treat (ITT)

To avoid any potential bias in the analysis, the primary outcome analysis will be conducted on the ITT population unless otherwise stated. Participants will be analysed according to the treatment arm they were randomised to and analysis will include all participants with outcome data.

7.5.2 Per protocol

The per-protocol analysis will be descriptive because there is no satisfactory way to define a per-protocol population for those in receipt of IY-B only. If the per-protocol population definition were based on IY-I and IY-T only we would only be removing people with higher scores at follow up 2 and 3 which would reduce the effects size compared to the ITT analysis and bias upwards the estimated impact on compliers because efficacy is demonstrated by a reduction in primary outcome.

Instead we will undertake a descriptive analysis comparing the characteristics of compliers compared to non-compliers. For example did compliers tend to be people with the greatest need (scores just over the eligibility threshold) or those with the higher scores. The characteristics investigated in this descriptive analysis will be the same as those used for the subgroups. This descriptive analysis will be an important input to the process evaluation.

7.6 Analysis of the primary outcome

7.6.1 Primary Analysis of the primary outcome

The ASQ:SE-2 is a set of questionnaires with different versions for different age groups. Consequently, different versions will be completed at each time point. The primary analysis will use raw ASQ:SE-2 scores as the scoring is the same across treatment arms and estimates will be easier to interpret. For ASQ:SE-2 either the 2 month or the 6 month questionnaire is administered at Follow-up 1 dependent upon the developmental age of the baby. If we observe an imbalance between arms in the number receiving the 2 months and 6 months versions we will adjust the score for those receiving the 2 months version by multiplying by 1.24. We have based the adjustment on the monitoring thresholds (25 and 30 for the 2 and 6 months surveys) and referral thresholds (35 and 45 for the 2 and 6 months surveys). The adjustment is midway between those required to preserve the monitoring threshold (30/25) and the referral threshold (45/35). If participants have completed both questionnaires, we will use the 6 months version and exclude them from the potential adjustment procedure.

The overall treatment effect will be estimated using a marginal model fitted using general estimating equations to account for the repeated measures with a Gaussian family, identity link, robust standard errors and an autoregressive covariance structure of order 1 AR(1). If the model does not converge using AR (1) we will use an unstructured correlation structure. The fixed effects will be stratifying variables (baseline ASQ:SE-2 score, baseline PHQ-9 score,

site⁴ and sex of child); potential confounders (ethnicity of the primary caregiver, marital status and highest level of education and follow up time (using an indicator variable for each time point)).

- The therapist induced clustering effect will not be fitted because the offer of IY-I and IY-T is conditional on outcome at FU1 and FU2 so clustering is confounded with treatment effect leading to biased estimation of the latter.
- The repeated measurements will be accounted for using a marginal model fitted using GEE because accounting for repeated measures using a mixed model inflates the type 1 error (random intercept only model) or gives a biased estimate of the treatment effect (random intercept and slope model).

These analysis decisions above were based on previous research (Candlish 2019) and simulation work undertaken during SAP development included in appendix B.

Descriptive statistics will be presented for ASQ:SE-2 and PHQ-9 at each time point (Appendix Table 6). Mean ASQ:SE-2 and PHQ-9 scores and 95% CIs by treatment arm will be presented in line plots. Spaghetti plots will also be used to visualise individual changes over time.

The following categories of the categorical variables will be used:

- Ethnicity of the primary caregiver: English/Welsh/Scottish/Northern Irish/British/Irish; Any other White background, Indian, Pakistani and Any Other ethnic group.
- Marital status: Married and living together; Cohabiting/living together; Other type of relationship and Not in a relationship or separated
- Highest level of education: Higher Education and Other (see Section 10.1 for details of how this will be defined).

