4.3 Blinding

The trial statistician will remain blind during the study until database freeze. At database freeze, the statistician will receive unblinded data. Full details of blinding can be found in the study protocol (v10).

5 Interim Analysis & Study Monitoring

The following committees have been established:

1. **Trial Steering Committee (TSC)** - consists of an independent chair, a member with early years expertise, an independent statistician, lay representatives (including a member of the Parent Advisory Committee) and the chief investigator. The role of the TSC is to provide supervision of the protocol and statistical analysis plan, to provide advice on and monitor progress of the study, to review information from other sources and consider recommendations from the DMEC. The TSC will meet at regular intervals as outlined in the TSC terms of reference. The TSC can prematurely close the trial following advice from the sponsor, funder, DMEC or TMG.
2. **Trial Management Group (TMG)** – The TMG consists of the chief investigator, trial managers and others as deemed necessary. The CI chairs the meetings at regular intervals as agreed by the group and oversees the day to day implementation of the trial in accordance with the terms of reference.
3. **Data Monitoring and Ethics Committee (DMEC)**- includes an independent chair and two independent members. The DMEC works in accordance with an agreed Charter, reviewing reports provided by the CTRU to assess the progress of the study, the safety data and the critical endpoint data as required.

These committees function in accordance with Sheffield CTRU standard operating procedures. Membership details of these committees are provided in the protocol (v10).

6 Data Collection

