10.2 Breastfeeding

At FU0, FU1 and FU2, participants are asked several questions on feeding their child. For the categorical variables, (e.g. Ever breastfed), the number and percentage of participants in each of the categories and the total number of observations will be presented. For the continuous variables (e.g. child's age when stopped breastfeeding) either mean and SD will be presented or median and IQR depending on the distribution of the data. The number of observations used in each calculation will be presented alongside the summaries.

11 Implementation of the Analysis Plan

This SAP will be used as a work description for the statistician involved in the trial. All analyses should ideally be performed by the same statistician (under the supervision of senior trial statistician) and consequently none of the investigators involved in the trial will perform any of the statistical analyses.

Initially, the data manager will provide blinded data for preliminary checks by the statistician. Following database freeze, unblinded data will be delivered to the statistician to define analysis sets and test statistical programs. Any queries will be communicated to the data manager prior to database lock, and any changes to the database during this time will be documented. The database will be locked after agreement between the statistician, data manager and study manager. It is expected that no data amendments should be required following database lock. However, if an amendment is required, the process is documented in CTRU SOP DM012.

12 References

- Buuren, S. van and Groothuis-Oudshoorn, K. (2011) 'mice:Multivariate Imputation by Chained Equations in R', *Journal of Statistical Software*, 45(3), pp. 1–67. doi: 10.18637/jss.v045.i03.
- Crittenden, P. M. (2010) *CARE-Index. Infants. Coding Manual*. Miami, FL, USA. Department of Health and Ageing, Canberra, A. (2006) 'Mental Health Information Development National Outcomes and Casemix Collection', (April).
- Farnfield, S. and Holmes, P. (2016) 'The Routledge Handbook of Attachment :

Assessment Mothers and infants Screening for maternal relationships at risk with the CARE-Index', (11237). doi: 10.4324/9781315770666.ch3.

Gamble, C. *et al.* (2017) 'Guidelines for the content of statistical analysis plans in clinical trials', *JAMA - Journal of the American Medical Association*, 318(23), pp. 2337–2343. doi: 10.1001/jama.2017.18556.

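### How the primary outcome is scored at FU1 depends on an undefined imbalance between arms that the statistician can judge only after unblinding

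*SAP*

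**What the plan says.** SAP section 7.6.1 sets the default scale: "The primary analysis will use raw ASQ:SE-2 scores as the scoring is the same across treatment arms and estimates will be easier to interpret". At FU1 the version depends on the baby's developmental age, and the section adds a conditional step: "If we observe an imbalance between arms in the number receiving the 2 months and 6 months versions we will adjust the score". When triggered, each 2-month-version score is multiplied by 1.24. The factor is derived openly from two pairs of cut-offs, 25 against 30 for monitoring and 35 against 45 for referral, and the section explains its choice as follows: "The adjustment is midway between those required to preserve the monitoring threshold (30/25) and the referral threshold (45/35"). Babies with both versions are scored on the 6-month one and left out of the rescaling.

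On access to allocation, section 4.3 says: "At database freeze, the statistician will receive unblinded data". Section 11 places this before lock: "Following database freeze, unblinded data will be delivered to the statistician to define analysis sets and test statistical programs". Queries can still be raised, and documented changes made, between freeze and lock.

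Sections 7.6.2 and 9.1.1 plan two sensitivity analyses on standardised scores (Z scores and percentages), calculated separately for each version. Section 7.7 compares arms at FU1 as an indicative analysis of the book and does not say whether the rescaling applies there.

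**The concern.** The factor is fixed in advance but the condition that switches it on is not. The SAP does not say how large an imbalance must be, how it is tested or who decides. An imbalance between arms cannot be seen without allocation, and the SAP names nobody other than the statistician to look for it. From freeze onwards the statistician holds version, score and arm together. Two different primary analyses are then available, and nothing written beforehand says which one applies.

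At stake are the credibility of the primary result, some inflation of type I error if the choice were influenced by results, and a shift in the FU1 comparison if a real imbalance is judged too small to act on. Nor does the SAP commit to reporting whichever scoring is not chosen.

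**Working it through.** **Inputs.** From the SAP: 606 participants at 5:1, so 505 and 101 (summary table); cut-offs 25/35 and 30/45 (section 7.6.1); FU1 mean 26, SD 10, correlation 0.4 between time points, effect 2.5 at FU1 and 3.46 overall (Appendix B); two-sided 5% level (section 7.1). Assumed: the share *p* of babies on the 2-month version at FU1, which the SAP does not give (range 10% to 50%), and that 26 is the mean on the 6-month version.

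**1. The plan's own factor.** 30/25 = 1.200; 45/35 = 1.286; midpoint (1.200 + 1.286)/2 = 1.243. The stated 1.24 reproduces.

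**2. Would the trigger come into play?** The standard error of the arm difference in version share is sqrt[p(1-p)(1/101 + 1/505)].
- p = 10%: SE 3.3 points; 95% chance range ±6.4; chance of exceeding 5 points 13%, of exceeding 10 points 0.2%.
- p = 20%: SE 4.4; ±8.5; 25% and 2.2%.
- p = 50%: SE 5.5; ±10.7; 36% and 6.7%.

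A visible difference is quite likely by chance alone, so the unstated cut-off decides which analysis is run.

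**3. Shift if raw scores are kept.** The gap between versions is 26 - 26/1.24 = 5.03 points. A 10-point imbalance shifts FU1 by 0.10 × 5.03 = 0.50 (0.43 with ratio 1.20, 0.58 with 1.286), and the mean of three visits by 0.50/3 = 0.17. Against Appendix B's effects these are 0.50/2.5 = 20% at FU1 and 0.17/3.46 = about 5% overall. The overall comparison is rough, because Appendix B simulates two follow-ups. A 5-point imbalance halves the shifts, to 0.25 and 0.08.

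**4. Type I error.** Null simulation with 10,000 runs per setting, 505 v 101, SD 10 and correlation 0.4. A simple mean over three visits stands in for the GEE. Simulation error is about sqrt(0.05 × 0.95/10,000) = 0.002.
- *Three-visit mean.* Rules fixed in advance (always raw, always rescaled, or a trigger fixed at 5 or 10 points) give 0.050-0.053. Taking whichever of raw and rescaled is significant gives 0.055-0.056 when the true scale ratio is 1.24, and 0.057-0.058 when it is 1.20 or 1.286.
- *FU1 alone.* Free choice gives 0.061 at p = 20% (fixed rules 0.048-0.051) and 0.071 at p = 50% (fixed rules 0.053-0.058). The fixed rules ran somewhat high in the 50% setting, so the added error is better read as about 0.061 - 0.051 = 0.010 and 0.071 - 0.058 = 0.013.

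**5. What 1.24 does to the cut-offs.** 25 × 1.24 = 31.0 against 30; 35 × 1.24 = 43.4 against 45. Neither is preserved.

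**The case against.** The strongest defence is that the trigger is a count of questionnaire versions, driven by the baby's developmental age and not by scores. The factor and the handling of double completers are fixed. Under randomisation any imbalance is chance error that averages to zero, and large imbalances, the ones most worth correcting, are both rare and the likeliest to be adjusted. Even deliberate selection moves the type I error of the overall test by well under one percentage point. The Z-score and percentage analyses will be run regardless and will show whether pooling versions matters.

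Most of this stands, and it limits the size of the problem. It does not remove it: the person counting versions will also hold outcomes by arm, and the sensitivity analyses do not settle which scoring is primary.

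Three stronger readings are tempting but unsupported:
- *That 1.24 must always be applied.* Raw scores are the stated default with a stated reason, the factor preserves neither cut-off, and every rule fixed in advance controls error about equally well.
- *That pooling unconverted versions clearly costs precision.* If scores scale by 1.24, so does the SD. The 2-month variance is then 100/1.24² = 65, and a 50:50 raw mix has variance (100 + 65)/2 + 0.25 × 5.03² = 88.8, below 100. If both versions have SD 10, rescaling lifts the 2-month variance to 153.8 and the mix to about 127, against 106.3 unconverted. The documents cannot say which holds.
- *That masking arm labels until lock would cure it.* With 5:1 allocation, arm size alone would reveal which arm is which.

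**Conclusion.** The point holds as a defect of pre-specification. Section 7.6.1, read with sections 4.3 and 11, leaves the choice between two primary analyses until after unblinding, on a criterion that is not defined. A reader might infer that the primary result is at serious risk, or that someone intends to choose by result; the documents support neither. The consequence for the overall estimate is small: about 0.17 points for a 10-point imbalance left raw, and type I error of at most about 0.058 under free choice. It is larger for the FU1 comparison (0.061-0.071), which section 7.7 itself treats as indicative.

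These sizes rest on the assumed version share, on treating 26 as the 6-month-version mean, and on a simplified simulation without covariates or missing data. The finding that the switch is undefined and judged after unblinding rests on none of them.

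**What to change.** Before allocation is released, replace the conditional sentence in section 7.6.1 with one unconditional rule for combining the two FU1 versions. The preferred rule keeps raw scores and includes an indicator for the 2-month version at FU1 in the model in all cases, with double completers counted as 6-month. This keeps the SAP's default scale and handles a mean difference between versions whatever the imbalance. It assumes that the version given is not affected by treatment, which should be stated. Always rescaling, or always using raw scores, would also remove the discretion.

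State that the same rule governs the FU1 ASQ:SE-2 analysis in section 7.7. Name the alternative (scores rescaled by 1.24, or unadjusted raw scores) as a sensitivity analysis to be reported whatever it shows.

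The cost is one extra model term or scoring step and a few lines of SAP wording. No extra data are needed, since the version completed must already be known to score the questionnaire.

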Trial participants	Parents of children aged 0 to 2 months at baseline, identified by children's centre staff, self-referral, Health Visitors and parent advisory committee. Level of need is assessed by completion of a self-report mental health questionnaire (parent) and a parent-report measure of child social and emotional development. Co-parents are included in measure completion (and in parent programmes if parent is allocated to intervention condition at each level of intervention dose).
Sample size	606 participants allocated in a ratio of 5:1 (intervention:control)

Follow-up	Measures are administered during home or community based visits at four intervals; baseline and three follow-ups (2, 9 and 18 months post baseline assessment).
Primary analysis	Repeated measures analysis on ASQ:SE-2 scores, comparing treatment and control groups to investigate the effectiveness of the proportionate delivery of the IY E-SEE steps/model overall on child social and emotional wellbeing.
Key Secondary analyses	Repeated measures analysis on PHQ-9 scores, comparing treatment and control groups to investigate the effectiveness of the proportionate delivery of the IY E-SEE steps/model overall on parent depression levels

1 Introduction

This document outlines the detailed statistical analysis plan (SAP) for the E-SEE main trial and is intended to be read in conjunction with the current study protocol (v10. This SAP is written in conjunction with the International Conference on Harmonisation topic E9 (ICH E9 Expert Working Group, 1999), guidance for the content of SAPs in clinical trials (Gamble *et al.*, 2017), applicable statistical standard operating procedures (SOPs) from the University of Sheffield Clinical Trials Research Unit (CTRU) and trial documents (Protocol and Data Validation Specification). The trial is conducted in accordance with Good Clinical Practice in Clinical Trials (ICH Harmonised Tripartite Guideline, 1996) and Medicine for Human Use (Clinical Trials) Regulations (UK Statutory Instruments, 2004).

This SAP will guide the Trial Statistician during the statistical analysis of all quantitative outcomes in order to answer the objectives of the study. It excludes the health economic and process evaluations (which will be described elsewhere).

All analysis will be performed in a validated statistical software package such as R (Team, 2012).

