1.2 Objectives

- a) Main effectiveness analyses of the intervention (compared to SAU) will be established at the follow-up 18-months post-baseline to address the key research questions relating to clinical outcomes.
- b) Economic evaluation: Establish cost-effectiveness using health, quality of life and service use data and IY intervention cost data, and explore the potential for long-term modelling of costs and benefits by extrapolating from trial outcomes.
- c) Comparative work: (1) Match and compare intervention participant outcomes with cohort general population data (e.g. Millennium Cohort Study); and (2) Conduct international comparison of outcomes with the complementary Irish trial, with IY-I and IY-T delivered in a non-proportionate universalism model, and explore potential opportunity (pending agreement from key stakeholders) to pool data from both studies to facilitate a meta-analysis.
- d) Establishing the importance of process: engagement, referral, and implementation fidelity rates will be at appropriate levels and effects of process, particularly fidelity, on outcome will be examined. Qualitative work objectives include establishing parent and co-parent perception of programmes and exploring the facilitative and inhibitive factors in service delivery.
- e) Establishing for whom the programme works best and how by exploring mediators and moderators of change.

This SAP is concerned with the main effectiveness analysis (objective A). Objective B is covered by the Health Economics Analysis; objective C is covered in an ancillary sub-study (ancillary sub-study D in the protocol); objective D is covered by the process evaluation and objective E will be covered in an additional ancillary sub-study following submission of the trial manuscript. The protocol also outlines ancillary sub-studies A to C (See page 24 in Protocol V10 11.06.2019). These ancillary sub-studies are covered in the appropriate sub-study reports.

2 Outcome measures

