This table will be repeated for Primary caregiver and co-parent PHQ-9 scores

[figure not shown]

Figure 2: Forest plot showing results from the primary analysis

[figure not shown]

Figure 3: Line plot of mean ASQ:SE-2 at each time point
This figure will be repeated for PHQ-9

Table 7: Results of the analysis of key secondary outcome 2

Outcome measure	n	Mean (SD) Intervention	n	Mean (SD) Control	n	Mean difference (95%CI)	Adjusted Mean difference (95%CI)*	p-value
ASQ:SE-2 at FU1	xx	xx.x(xx.x)	xx	xx.x(xx.x)	xx	xx.x(xx.x-xx.x)	xx.x(xx.x-xx.x)	0.xxxx
ASQ:SE-2 at FU2 in the subgroup of parents with PHQ-9 score >=5 OR Child ASQ:SE2 score>= Monitoring Zone	Xx	xx.x(xx.x)	xx	xx.x(xx.x)	xx	xx.x(xx.x-xx.x)	xx.x(xx.x-xx.x)	0.xxxx
ASQ:SE-2 at FU3 in the subgroup of parents with PHQ-9 score >=5 OR Child ASQ:SE2 score>= Monitoring Zone	xx	xx.x(xx.x)	xx	xx.x(xx.x)	xx	xx.x(xx.x-xx.x)	xx.x(xx.x-xx.x)	0.xxxx

This table will be repeated for primary care givers and co-parents (PHQ-9 scores)

iv. Analysis of secondary outcomes results

Table 8 : EQ5D-5L for primary care-givers

	n	Mean (SD) Intervention	n	Mean (SD) Control	n	Mean difference (95%CI)	Adjusted Mean difference (95%CI)*	p-value
Primary carer EQ5D-5L								
Baseline	xx	xx.x(xx.x)	xx	xx.x(xx.x)	xx	xx.x(xx.x-xx.x)		
FU1	xx	xx.x(xx.x)	xx	xx.x(xx.x)	xx	xx.x(xx.x-xx.x)	xx.x(xx.x-xx.x)	0.xxxx
FU2	xx	xx.x(xx.x)	xx	xx.x(xx.x)	xx	xx.x(xx.x-xx.x)	xx.x(xx.x-xx.x)	0.xxxx
FU3	xx	xx.x(xx.x)	xx	xx.x(xx.x)	xx	xx.x(xx.x-xx.x)	xx.x(xx.x-xx.x)	0.xxxx

*adjusted for baseline ASQ:SE-2 score, baseline PHQ-9 score, sex of child and recruitment site and baseline measure
 This table will be repeated for secondary outcome data collected at FU2 and FU2

Each Secondary outcomes will be reported in separate table showing outcome by time-point in a similar manner to table

[figure not shown]

Figure 4: Line plot showing mean secondary outcome scores

v. Subgroup analysis results

Table 9: Results of subgroup analysis

Subgroup	n	Mean (SD) Intervention	n	Mean (SD) Control	n	Mean difference (95%CI)*	p-value*
TBC	xx	xx.x(xx.x)	xx	xx.x(xx.x)	xx	xx.x(xx.x-xx.x)	0.xxxx
	xx	xx.x(xx.x)	xx	xx.x(xx.x)	xx	xx.x(xx.x-xx.x)	
	xx	xx.x(xx.x)	xx	xx.x(xx.x)	xx	xx.x(xx.x-xx.x)	
	xx	xx.x(xx.x)	xx	xx.x(xx.x)	xx	xx.x(xx.x-xx.x)	0.xxxx
	xx	xx.x(xx.x)	xx	xx.x(xx.x)	xx	xx.x(xx.x-xx.x)	
	xx	xx.x(xx.x)	xx	xx.x(xx.x)	xx	xx.x(xx.x-xx.x)	0.xxxx
	xx	xx.x(xx.x)	xx	xx.x(xx.x)	xx	xx.x(xx.x-xx.x)	
	xx	xx.x(xx.x)	xx	xx.x(xx.x)	xx	xx.x(xx.x-xx.x)	

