Appendix B: E-SEE Primary Outcome – methods comparison

Proposed Primary Analysis

For our primary analysis, we propose to ignore the clustering by treatment group, as it is not possible to account for it appropriately in the methods we have explored. This is also current practice in the wider community.

Background

The E-SEE intervention has three distinct phases. In stage 1, all participants in the treatment arm get a self-help intervention book and in stages 2 and 3, participants with interim outcomes above a threshold are eligible for a group therapy.

The objective of the primary analysis is to estimate the impact of the intervention as a whole rather than the specific stages. In many ways, E-SEE is similar to stepped care treatments where higher intensity treatments are available to those unresponsive to a lower intensity treatment. The difference here is that the higher intensity E-SEE interventions is group based, which may induce clustering (“within-arm partial nesting” in the literature). The recent systematic review arising from the E-SEE sub-study (Candlish et al, 2019) found it is common practice to ignore such treatment induced clustering in the statistical analysis. This seems to contrast with the recommendation that trials with single arm treatment induced clustering should account for clustering in the analysis (Candlish et al. 2018). In Chapter 5 of her PhD thesis Candlish explored a number of approaches to analyse a simple within-arm partially nested trial. The thesis demonstrated that random assignment of a treatment group subset to a stepped up group based treatment then adjusting for clustering was appropriate. However, with targeted allocation (as in a proportionate intervention such as ESEE) adjusting for clustering gave biased estimates of the treatment effect even under the null. The thesis also explored linear regression with fixed effects only with and without cluster robust standard errors.

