- The outcomes under the null at FU1 and FU2 vary according to a normal distribution with mean 26 and 36 respectively and standard deviation (s) of 10 (before clustering) for each time point;
- An overall effect size of 3.46 (2.5 at FU1 and 15 for those stepped up at FU2);
- A correlation (τ) of 0.4 between time points;
- 13 clusters sized between 2 and 12⁵ as in ESEE (see appendix C);

The number of samples and values of ICC considered was lower for the more complex models because the time taken to estimate the model for each sample was prohibitively high.

⁵ Actual cluster sizes were: 2, 2, 2, 3, 6, 6, 6, 6, 7, 7, 8, 9 and 12

Outcomes for the three time points are generated using two stages. First by simulating values from a normal distribution with fixed mean and standard deviation reduced to account for time correlation [$s\sqrt{(1 - \tau)}$] and second, by adding an individual component common to each of the individual's three time points with mean 0 and standard deviation [$s\sqrt{\tau}$].

We simulate the assumed intra-cluster correlation (ρ) by adding a mean cluster effect to each member of the cluster at FU2 with mean 0 and variance σ_u^2 such that:

$$\frac{\sigma_u^2}{\sigma_u^2 + \sigma_e^2} = \rho, \text{ i.e. } \sigma_u = s\sqrt{\rho\sqrt{(1 - \tau)}}$$

The simulations used STATA.

Results

[figure not shown]
Charts are in appendix D and results are summarised in Table A1. Table A1 shows that selecting the most appropriate model will require a trade-off between bias and precision. Model 1 gives highly biased estimates and can be discounted immediately. Model 3 (random intercept and slope with adjustment for unequal variance) best controls for precision with type I error appropriately controlled (5%) and type II error increasing as ICC and total variance increases; but gives biased estimates of the treatment effect. Unbiased estimates are given by models 2, 4 and 5 and while they all exhibit similar levels of type II error, model 5 gives the best control for type I error and is our preferred model for the primary analysis because we believe that an unbiased estimate is more important than precision.

Table A1: Results of methods comparison

		Effect	Type 1	Power	Runs
Full mixed model	1 Random effects for time and clusters ⁶ ; exchangeable correlation, Satterthwaite SE	2.5 (biased)	0.05	0.83	100
Naïve Mixed model	2 Random intercept	3.46	0.08	0.99	500

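### Objective 1.2(a) places main effectiveness at 18 months, but the primary model in 7.6.1 gives one effect pooled over 2, 9 and 18 months, and the SAP does not reconcile the two

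*SAP*

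**What the plan says.** **Objective.** SAP 1.2(a): "Main effectiveness analyses of the intervention (compared to SAU) will be established at the follow-up 18-months post-baseline". The same section says that this SAP is concerned with that objective. The summary table gives the visits as "baseline and three follow-ups (2, 9 and 18 months post baseline assessment").

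**Primary model.** SAP 7.6.1: "The overall treatment effect will be estimated using a marginal model fitted using general estimating equations to account for the repeated measures". The working correlation is AR(1), with an unstructured fallback if the model does not converge. The listed fixed effects are baseline scores, site, sex of child, three potential confounders and "follow up time (using an indicator variable for each time point"). No arm-by-time term appears.

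**Stated aim of pooling.** Appendix B: "The objective of the primary analysis is to estimate the impact of the intervention as a whole rather than the specific stages".

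**What is planned for ASQ:SE-2 by visit.** Section 7.6.1 and Table 6 give descriptive statistics, and line plots show means with confidence intervals. Section 7.7 plans a regression at FU1 in all participants. At FU2 and FU3 the regressions cover only parents and children above the need threshold, and the SAP itself calls this set of analyses non-randomised and indicative.

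**Secondary outcomes.** Section 7.8 applies the primary approach to PSoC, EQ5D-5L and CARE Index. The Table 8 shell has an adjusted difference and a p-value in each of the FU1, FU2 and FU3 rows, and the note beneath it says: "Each Secondary outcomes will be reported in separate table showing outcome by time-point".

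**The concern.** The steps of the intervention arrive over time (SAP 4.2). At FU1 families in the intervention arm have had the book. IY-I is offered after FU1 and IY-T after FU2. Only FU3 can therefore reflect all three levels named in the primary outcome definition (2.1), and 1.2(a) reads as if FU3 is where the effect will be judged.

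A coefficient common to the three visits is a weighted average of three visit-specific differences. If the effect changes over time, that average is not the 18-month effect, and its weights come from the working correlation rather than from the question. The trial could then be described as positive or null at 18 months without the primary model having estimated that difference. The error can go either way: a late effect is diluted, and an early effect that fades is carried forward.

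**Working it through.** **1. The SAP's own figure.** Appendix B assumes "An overall effect size of 3.46 (2.5 at FU1 and 15 for those stepped up at FU2").

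- The 13 listed cluster sizes sum to 76 stepped-up participants.
- The simulated arm size is not given in the readable text. Assume 505 in the intervention arm (5/6 of 606), so the stepped-up fraction is p = 76/505 = 0.1505.
- FU2 effect = 2.5(1 − p) + 15p = 4.38.
- Pooled effect = (2.5 + 4.38)/2 = 3.44, against 3.46 stated. With 495 in the arm it is 3.46.

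So 3.46 is the equal average of the two visit effects. The last-visit effect that it implies is 2 × 3.46 − 2.5 = 4.42, and 3.46/4.42 = 0.78. The pooled figure is 0.96 points below the last-visit effect in that scenario.

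**2. Weights in the planned three-visit model.** With complete data, a common variance and visit indicators, the weights on the visit differences are proportional to the row sums of the inverse working correlation matrix. For AR(1) at three visits they are (1, 1 − ρ, 1)/(3 − ρ). The value ρ = 0.4 is from Appendix B; 0.2 and 0.6 are assumed to show a range.

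| ρ | FU1 (2 months) | FU2 (9 months) | FU3 (18 months) |
|---|---|---|---|
| 0.2 | 0.357 | 0.286 | 0.357 |
| 0.4 | 0.385 | 0.231 | 0.385 |
| 0.6 | 0.417 | 0.167 | 0.417 |

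FU1 and FU3 always have equal weight.

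**3. What the model would report for assumed effect patterns.**

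| Effect at FU1, FU2, FU3 | Pooled, ρ = 0.2 / 0.4 / 0.6 | 18-month effect |
|---|---|---|
| 0, 0, 3.46 | 1.24 / 1.33 / 1.44 | 3.46 |
| 2.5, 4.42, 4.42 | 3.73 / 3.68 / 3.62 | 4.42 |
| 5, 2.5, 0 | 2.5 / 2.5 / 2.5 | 0 |

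**4. Dependence on the fallback.** Under an unstructured matrix with assumed correlations of 0.2 (FU1–FU2), 0.2 (FU1–FU3) and 0.6 (FU2–FU3), the weights are 0.43, 0.29 and 0.29. The quantity estimated would then depend on whether AR(1) converged.

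**5. Is the 18-month difference estimated elsewhere?** The sensitivity analyses in 7.6.2 change the score standardisation and the handling of missing data, not the target. The by-visit outputs for ASQ:SE-2 at FU3 are descriptive, or are restricted to the need subgroup in 7.7. No passage gives a modelled FU3 difference in all randomised participants.

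**6. Table 8.** Its shell has three adjusted differences with three p-values. The approach that 7.8 borrows from 7.6.1 yields one.

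**7. Price of the 18-month contrast.** At exchangeable correlation 0.4, the standard error of the three-visit mean relative to one visit is √((1 + 2 × 0.4)/3) = 0.775, so the 18-month standard error is 1/0.775 = 1.29 times as large. Under AR(1) at 0.4 the relative variance of the equal average is (3 + 2(0.4 + 0.4 + 0.16))/9 = 0.547, which gives a ratio of 1.35.

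**The case against.** **Pooling is deliberate.** The summary table describes a repeated measures analysis of the model overall, 2.1 lists ASQ:SE-2 at all time points without singling out 18 months, and Appendix B says that the aim is the whole intervention. The protocol sentence quoted in 7.10 also names a treatment and a time effect without an interaction. Section 1.2(a) could mean only that the analysis takes place once the 18-month data are in. This stands: the model does not fail its own aim of an overall effect. What remains is that 1.2(a) can equally be read as naming the 18-month contrast, and the SAP does not say which is meant.

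**The list of model terms is incomplete.** The arm term itself is not listed, so the absence of an interaction is an inference. It is a sound one, since a single overall effect is the stated output.

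**The 18-month comparison is visible.** Means by arm at FU3 are tabulated and plotted. They are unadjusted summaries, not an adjusted difference with an interval and a test.

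**Precision.** Making FU3 primary costs precision, and the sample size basis lies in the protocol, so one cannot say here whether 606 supports it. This also stands, and it is why the choice of primary contrast is left open below.

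**Appendix B.** A reader might infer that pooling a changing effect explains the estimates marked as biased there, because 2.5 for model 1 equals the FU1 effect. The documents do not support this. Models 2, 4 and 5 return 3.46 from the same changing effect, and Appendix B reports bias from adjusting for clustering under targeted allocation even under the null.

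**Conclusion.** The conflict is real and unresolved: 1.2(a) reads as an 18-month target, 7.6.1 delivers a pooled one, and no modelled all-randomised 18-month difference in the primary outcome is planned. With complete data and AR(1) correlation between 0.2 and 0.6, FU3 carries 36% to 42% of the weight, the same as the book-only visit. A 3.46-point effect confined to 18 months would be reported as about 1.2 to 1.4.

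The 78% ratio illustrates dilution in the SAP's own scenario. A reader might take it as the share of the 18-month effect that this trial would report, but the simulation has two visits and one group step, and its last visit is not FU3. A percentage for the trial itself would need an 18-month effect that the SAP does not give. A reader might also conclude that the pooled analysis is invalid. The documents do not support that either, because an overall effect is a legitimate and stated aim. The mismatch between Table 8 and 7.8 holds however 1.2(a) is read.

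**What to change.** Before the statistician receives unblinded data at database freeze:

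- In 7.6.1, list the arm term and add arm-by-follow-up-time terms to the same GEE. Use the same model for PHQ-9, PSoC, EQ-5D-5L and CARE Index.
- From that one fit report the adjusted FU3 difference with its 95% confidence interval, the FU1 and FU2 differences, and the equally weighted average of the three as the overall effect. The weights are then fixed in advance and do not depend on the working correlation or its fallback.
- State which contrast is primary: either FU3, as 1.2(a) reads, or the overall average with 1.2(a) amended to match.

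The cost is two extra parameters per model and some SAP wording; no new data are needed. The 18-month interval will be wider, with a standard error about 1.3 times that of the overall average at correlation 0.4. If FU3 is made primary, the sample size basis in the protocol should be checked against it. Table 8 can then be filled as drawn.
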